Primary outcome: Loneliness as measured by the 6-item De Jong Gierveld Loneliness Scale; secondary outcomes include depression and anxiety. All three outcome measures yield continuously distributed summary scores with interval scale properties; and all three outcomes are measured both prior to and after the intervention period. This design permits us to examine whether the phone-based loneliness intervention differentially improves the loneliness scores over that of the control group. Mixed linear models/ hierarchical linear models will be adopted to model pre to post change in loneliness at level-1; we will test whether the pre to post changes in loneliness differs as a function of treatment assignment at level-2. These analyses will control and test for differences in the magnitude of the treatment effect across the 6 callers at level-2. Participant ratings pertinent to perception of the caller's empathy/impact measured by CARE as part of the sub-study will also be included at level-2. A similar analytic approach will be adopted to test if the phone-based loneliness intervention also affects depression and anxiety ratings from pre to post-intervention. The rank-order stability of loneliness, depression, and anxiety scores tend to be moderate to large; and moderate to high correlations affect statistical power positively. A sample size of 125 participants in each group can detect a small effect size for the interaction of group with pre to post-difference (f=.09 to f=.10) with 80% to 90% power respectively using an alpha of .05 assuming a correlation of .60 between the pre and post measurements. The sample size of 125 participants in each group has been established to adequately power the study to provide information on the effect of the intervention to inform future planned studies. Mixed linear models will permit the estimation of these models when there is missing data while accounting for greater similarity in therapeutic effects in subsets of participants due to shared callers who deliver the intervention. The exploratory analyses pertinent to perception of the impact/approach of the caller by the participant will be incorporated into these primary analyses and will inform whether the perception of effectiveness predicts the magnitude of change from pre to post intervention.

8

Funding and Regulatory Oversight

Check all agencies that fund or hold regulatory oversight over the research activities.						

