Household Status	Redcap Survey	Baseline						
Self-reported medical conditions with date of diagnosis Redcap Survey post-intervention								
Intervention Satisfaction	Redcap Survey	Post-intervention (for intervention arm only)						
Loneliness	De Jong Gierveld Loneliness Scale (6-item) (standardized, published)	Baseline and						

		post-intervention
oneliness/Isolation	UCLA Short Scale for Measuring Loneliness in Large Surveys	Baseline and
	(Standardized, published)	
Depression	PHQ-8	Baseline and
	(Standardized, published)	post-intervention
Anxiety	GAD7	Baseline and
	(Standardized, published)	post-intervention
Social Isolation & Connection	Lubben Social Network Scale	Baseline and
	(Standardized, published)	post-intervention
Consultation & Relational Therapy	CARE Measure	Post-intervention (for
	(Standardized, published)	intervention arm only)
Quality of Life	Health Status and Quality of Life	Baseline and
	SF12 (Standardized, published)	post-intervention
o-Study Exploration on Importance of	Volunteer Caller Empathy:	
utcome Measures	Collection Tool	Frequency
emographics (Name, Age, Sex, Race,	Redcap Survey	Baseline

Empathy	Toronto Empathy Questionnaire	Baseline and
	(Standardized, published)	post-intervention

c) Secondary data

No secondary data.

 d) Where each activity will take place, duration of each, and who will do each All activities of the study will take place telephonically.
 Roles: Research Manager (not blinded to study arm assignment), Research Associate (blinded to group assignment as this role will be collecting the baseline and post intervention surveys), Program Associate/Caller (not-blinded, only delivers calls to the

Language)

Procedures

intervention arm).

- i. Recruitment approximately 5 minutes per call, by Research Associate
- ii. Consenting 30 minutes per participant, conducted by Research Associate
- iii. Baseline measurement 30 minutes per participant, conducted by Research Associate
- iv. Intervention calls 5 days/week M-F for 4 weeks taking 5-10 minutes per call, conducted by Program Associate/Caller.
- v. **Post-intervention measurement** -30 minutes per participant, conducted by Research Associate.

e) Time commitment of participants.

i. Intervention arm

Cumulative number of hours for the intervention calls is approximately 3 and 1/3 hours (20 calls lasting approximately 10 minutes each).

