	-	 Primary study: Increasing numbers of older adults are living alone in the community. Given potential deaths of spouses, family and friends, retirement, and age-related physical changes, the aging adult becomes high-risk for social isolation and loneliness, both of which can contribute to poor health outcomes. Findings from this study will help to inform potential intervention development to address this growing health issue. Sub-study exploration: Growing evidence suggests that the degree of empathy perceived within a relationship contributes to desired, successful outcomes of the relationship. By exploring the self-reported empathy levels of the caller, the perceived empathy levels by the participant, and the achieved outcomes of the primary study intervention, it could help inform future programs about the characteristics most important to identify in program personnel initiating the social connection, and the importance of such to the program's effectiveness 					
		No potential for direct benefits to participants					
Direct Benefit	\boxtimes	Describe potential for direct benefits to participants.					
		Participants in the intervention arm of the primary study could					

benefit from the intervention by reducing their level of loneliness, depression, anxiety, and social isolation.
There is no direct benefit to the sub-study participants.

38

Risks

_ Greater than Minimal Risk Study

Complete the Data Safety and Monitoring Plan section below.

Research related risks only pertain to risks associated with procedures required by the study; do not include risks of any procedures that the participant would undergo if not participating in the study.

Describe the risk(s) associated with the research.

The measures are minimal risk.

Describe the risk mitigation plan

Although there are minimal risks to participating in this part of the study, there is potential for discomfort sharing personal information about themselves. We have indicated in the consent form that the participants do not have to answer any questions that make them feel uncomfortable and they can stop the interview and the intervention calls at any time. There is also the risk of loss of confidentiality. We will follow HIPAA security standards in data transition and storage to minimize this risk.

39

Data Safety and Monitoring Boards (DSMBs) and Plans (DSMPs)

□ This study will have a DSMB.

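### Missing post-intervention loneliness is in effect predicted from arm and baseline loneliness alone, leaving the group-by-time contrast open to a possible, probably modest, attrition bias that baseline data already collected could reduce

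*Combined protocol and SAP*

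**What the plan says.** The primary outcome in the Data Analysis section is "Loneliness as measured by the 6-item De Jong Gierveld Loneliness Scale", measured before and after the intervention. Change is modelled at level 1, and "we will test whether the pre to post changes in loneliness differs as a function of treatment assignment at level-2". Caller and the CARE rating are the other level-2 terms named. Depression and anxiety get a similar analysis in models of their own.

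On missing data, the section says: "Mixed linear models will permit the estimation of these models when there is missing data". It gives no missing-at-random assumption, expected attrition, auxiliary variable or sensitivity analysis.

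The outcome measures table under Procedures lists PHQ-8, GAD-7, Lubben and SF-12 (the row "Health Status and Quality of Life") at baseline and post-intervention. The UCLA scale is also listed with a baseline measurement, and age and household status are listed at baseline. Procedures places baseline measurement before randomisation. CARE is post-intervention and intervention arm only.

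On leaving the study, the Risks section says participants are told that "they can stop the interview and the intervention calls at any time". Early Withdrawal allows withdrawal at any point.

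**The concern.** A likelihood-based mixed model is valid when missingness depends only on what the model contains. Here that is little. With a single pre and a single post value, a participant lost before the post survey contributes a baseline loneliness score and an arm label. Caller cannot inform a control's missing score. CARE is due at the post-intervention stage, so a participant lost before then has no CARE rating either.

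Depression, health and living situation plausibly affect both who is lost and how loneliness changes; the Study Background itself links loneliness to depressive symptoms. The arms also differ in ways that could make loss differ. One is offered up to 20 calls and the other none, and the $10 completion gift card is described for controls only. If more depressed intervention participants are the ones lost, the contrast shifts towards benefit. A larger sample does not average such a shift away.

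**Working it through.** **Scale of the design effect.** The plan says "A sample size of 125 participants in each group can detect a small effect size", "using an alpha of .05 assuming a correlation of .60 between the pre and post measurements". In a 2×2 group-by-time layout the between-arm difference in change is d = 4f in SD units, so f = .09 and .10 mean 0.36 and 0.40 SD.

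Reproducing the stated power (80% and 90%) with λ = f²·N·m/(1−ρ), N = 250, m = 2, ρ = .60, df 1 and 248, two-sided alpha assumed:

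- f = .09: λ = .0081 × 500 / .40 = 10.125, power 88.7%.
- f = .10: λ = .0100 × 500 / .40 = 12.5, power 94.1%.

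The stated figures are not reproduced. They err on the conservative side. That is a separate matter; only the 0.36–0.40 SD scale is used below.

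**Standard error of the contrast, complete data.** √(2 × 2(1−ρ)/125) = √(1.6/125) = 0.113 SD; about 0.12 with missing scores.

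**How the bias arises.** Write post loneliness as a + b·(baseline loneliness) + β·(baseline PHQ-8) + error, in SD units. Let R be the part of PHQ-8 not explained by baseline loneliness. Omitting PHQ-8 gives approximately

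bias ≈ β × (mean R in intervention completers − mean R in control completers).

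It is zero if β = 0, if dropout is unrelated to R, or if the two completer means agree.

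**Inputs.** From the plan: ρ = .60. Assumed, because the documents give none: PHQ-8/loneliness correlation .5; β = .1 to .3; where dropout depends on PHQ-8, its log-odds change by 1 per SD; 10–20% missing; no true effect. Large-sample simulation (1.5 to 2 million per arm) gave the .2 and .3 columns. The .1 column is half the .2 column, since the bias is proportional to β. Entries are SD towards benefit.

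| Dropout pattern | Missing, intervention v control | β = .1 | β = .2 | β = .3 |
|---|---|---|---|---|
| Same mechanism, same rate | 15% v 15% | 0 | 0.000 | 0.000 |
| Same mechanism | 20% v 10% | 0.006 | 0.012 | 0.020 |
| Intervention arm only | 15% v 15% | 0.009 | 0.018 | 0.030 |
| Intervention arm only | 20% v 10% | 0.014 | 0.027 | 0.042 |
| Opposite in the two arms | 15% v 15% | 0.020 | 0.041 | 0.059 |
| Opposite in the two arms | 20% v 20% | 0.027 | 0.053 | 0.080 |

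Check on the formula: 0.027/.2 = 0.135 and 0.042/.3 = 0.14, so both imply nearly the same gap in mean R.

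**A second set of assumptions** (correlation .4, partial correlation .1–.3, odds ratio for missingness .5 to 2 per SD, 10–30% missing) gives 0 with matched arms, 0.003–0.011 SD with one mechanism and 20% v 10% missing, and 0.006–0.045 SD when the mechanism differs by arm.

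**In context.** 0.04/0.36 = 11% of the smaller design effect, and 0.04/0.113 = 0.35 standard errors. Two-sided type I error becomes Φ(−1.96+0.35) + Φ(−1.96−0.35) ≈ 0.054 + 0.010, about 6% instead of 5%.

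**With baseline PHQ-8 in the model**, bias was 0.002 SD or less in the intervention-only and opposite-mechanism rows. That follows from the set-up, because dropout was generated from PHQ-8 alone. It shows that conditioning works when the driver of dropout has been measured, not that PHQ-8 is the driver.

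**The case against.** A mixed model fitted to all observed data is a standard, valid method under missing at random, and no passage shows that this assumption fails. In the most natural case, where more depressed clients are lost from both arms at similar rates, the bias is nil. The burden argument is also weaker than it looks. Participants may cut calls to two a week. Stopping the calls is not the same as missing the post survey, which is a separate call by a different staff member. Regular contact could even improve retention. All of this stands, and it is why the bias is only possible and its direction unknown.

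A reader might infer that the contrast is already biased in favour of the calls, by as much as 0.08/0.36 = 22% of the design effect. The documents do not support that. They state no attrition rate or mechanism. The 0.08 SD figure needs more depressed people to leave one arm while less depressed people leave the other, which nothing in the plan suggests.

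What the objection leaves untouched is that relevant baseline measurements are in hand and unused, and that the model's missing-data assumption is unstated and untested.

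**Conclusion.** The concern holds as an exposure to bias. The loneliness model's only protection against missing post scores is arm and baseline loneliness, although relevant baseline variables are collected before randomisation. Under the assumed inputs the plausible bias runs from 0 to about 0.04 SD, at most about a third of a standard error, with 0.08 SD as an upper bound. That would not invalidate the trial.

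The conclusion rests on assumed attrition, an assumed link between PHQ-8 and post loneliness beyond baseline loneliness, and a difference between arms in rate or mechanism. Baseline covariates remove only the part of the bias they explain. Dropout that depends on the unobserved post score would remain, and the plan has no sensitivity analysis for it. The change is worth making because it costs little and is best fixed before outcome data are seen.

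**What to change.** In the Data Analysis section:

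- **Loneliness model.** Prespecify baseline PHQ-8, SF-12 summary scores, age and household status, each with its interaction with time. State the missing-at-random assumption given these variables, and fix the household-status categories in advance, since the plan does not define them.
- **Depression and anxiety models.** Use the same list plus baseline loneliness, but omit the baseline value of the outcome being modelled. PHQ-8 must not be a covariate in the PHQ-8 model: its baseline value is already the time-0 response, and a covariate-by-time term would reproduce it exactly.
- **Separate sensitivity analysis** for dropout that depends on the unobserved score. Use multiple imputation by arm from these baseline variables plus baseline UCLA, repeated with a stated shift of 0 to 0.5 SD worse for missing intervention-arm scores. Post-intervention UCLA would add little, because it belongs to the same survey that was missed.

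The cost is a few sentences, a few of roughly 248 degrees of freedom and a little more analysis work. No new data, participants or procedures are needed.

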Control Arm: 125 MOW clients will be randomized to a control group that will not receive the intervention calls. The control group will receive calls from a member of the research team at the beginning of the study to collect baseline survey data and at the post-4-week period to collect post-study survey data. Participants in the control group will receive a \$10 HEB or Visa gift card upon completion of the study.

Timeline: 1) Baseline data collection. 2) Week 1-4 – intervention is delivered. 3) Post intervention data collection. We expect the intervention to begin 1-2 days after baseline. And we expect the post intervention data collection to occur 1-2 days after the end of the last call.

Other goals of study:

In addition to the primary aim of the study, we will also be collecting information to inform future studies including a current IRB approved program scheduled to begin after the summer (whenever COVID guidelines permit) on the impact of medically-tailored meals and social connection on Hemoglobin A1C and other health measures for diabetics in the MoW program. Additional goals include:

- a. Impact of intervention on the validated tools we will use for the future study Depression/PHQ-8, Anxiety GAD-7
- b. Comparison of the primary loneliness tool used in this study, the 6-item De Jong Gierveld Loneliness Scale, with the results from the short-form UCLA loneliness tool that is currently

planned for our longer study.

Sub-study exploration goals:

A second, but related area of exploration within this study will allow us to begin understanding the impact of caller empathy on outcomes, and self-reported alignment of empathy level compared to perceived empathy as reported by call recipient. This embedded sub-study requires that the callers, members of the research team delivering the intervention in the primary study, are consented and measurements collected from them in their roles as study participants within the sub-study.

- c. Perception of caller's approach and impact (CARE measure, completed by intervention arm of main study)
- d. Assessment by each caller of their empathetic ability via the Toronto Empathy Questionnaire.

Data Analysis

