Cumulative number of hours for the baseline (which will include the consent process and any questions and 4-week post intervention measurement collection for the participant is approximately 1.5 hours.

ii. Control arm

Cumulative number of hours for the baseline and 4-week post intervention measurement collection for the participant is approximately 1.5 hours.

Sub-study exploration

a) Sub-Study Procedures in sequential order.

i. Consent-

As members of the research team in the role of callers for the primary study, each Program Associate/Caller will learn of the goals of the substudy and their role as participants for the sub-study exploration. The consent form will be shared with them via email. These members have already been identified as volunteer callers for the main study. Participation in the sub-study is completely optional and will not impact their role as a member of the research team in the primary study, nor will it impact their relationship with UT moving forward. They will be given the opportunity to ask questions about the sub-study via telephone or email. The consent will be obtained via electronic signature by a member of the research team.

ii. Measurement collection-

Procedures
Program Associates/Callers for the primary study will be asked to complete the Toronto Empathy Questionnaire prior to the
empathy/engagement training or placing any calls for the primary study
intervention and after completion of the 4 weeks of calls
intervention and after completion of the 4 weeks of calls
iii. Empathy/Engagement training
A limited, approximately one hour session, will be provided to the
Program Associates/Callers that reviews the role of empathy in building
connections with others and provides suggestions on tools that could be used to effectively engage with the intervention arm participants of the
main study. This limited training will be standardized across the course of
the trial.
b) All research measures
Toronto Empathy Questionnaire (standardized, published)
c) Secondary data
None
d) Where each activity will take place, duration of each, and who will do each
All activities will take place virtually, either via email or telephonically.
Consenting – 10 minutes per participant, conducted by member of the research
team
Measurement Collection – 5 minutes per participant per survey, collected by a
member of the research team
e) Time commitment of participants
Program Associates/Caller participants – 20 minutes

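### The CARE rating comes from the same post-intervention survey session as the outcomes, so its link with change is a concurrent association and cannot show an effect of caller empathy

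*Combined protocol and SAP*

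**What the plan says.** Under Sub-study exploration goals, the sub-study "will allow us to begin understanding the impact of caller empathy on outcomes". Two instruments are named there: CARE ("CARE measure, completed by intervention arm of main study") and the callers' self-completed Toronto Empathy Questionnaire.

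The Data Analysis section uses only the first. Participant ratings of caller "empathy/impact measured by CARE as part of the sub-study will also be included at level-2" of the mixed model for pre-to-post change, and this analysis "will inform whether the perception of effectiveness predicts the magnitude of change from pre to post intervention". The section calls it exploratory but places it within the primary analyses. The Toronto score is not mentioned there.

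On timing, the measures table under Procedures lists CARE at post-intervention only, for the intervention arm only. Loneliness, PHQ-8 and GAD-7 are listed at baseline and post-intervention. Callers complete the Toronto questionnaire before "empathy/engagement training or placing any calls for the primary study", and again after the four weeks of calls.

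On use, the Benefits section says that self-reported empathy, perceived empathy and outcomes together could help show which characteristics to look for in programme staff.

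**The concern.** CARE does not precede the change it is said to predict. It and the post half of the change score come from the same person on the same occasion. A participant who feels less lonely or in better spirits that day may rate the caller higher and also report less loneliness. A real effect of caller empathy would give a coefficient of the same sign, and nothing in the Data Analysis section tells the two apart. Restricting the analysis to the intervention arm, or allocating callers at random, would not remove the problem.

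At stake is what the sub-study may conclude. Choosing staff by their characteristics needs evidence about callers, and a same-occasion correlation within participants does not supply it. The empathy measure with the right time order, the callers' Toronto score from before training and calls, has no stated role in the analysis.

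**Working it through.** **Same session.** The documents do not say this in so many words. It follows from three places:
- Design gives each participant two survey calls.
- The measures table makes CARE post-intervention only.
- Procedures, part d, gives one 30-minute post-intervention measurement session, which Timeline expects 1-2 days after the last call. CARE has no other slot.

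**The plan's own figure.** None is given for the CARE analysis. The stated power concerns the group-by-time interaction and does not bear on this point.

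**Inputs.** From the plan: n = 125 in the intervention arm, pre-post correlation ρ = .60, α = .05 (taken as two-sided). Assumed: a state s, specific to the post session and independent of baseline, loads L on CARE and −L on post loneliness. All variables have unit variance, and CARE has no causal effect.

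**Model as planned.** A level-2 predictor of pre-to-post change amounts to correlating CARE with (post − pre).

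- corr(CARE, post) = −L²
- SD of change = √(2(1 − ρ)) = √0.8 = 0.894
- corr(CARE, change) = −L²/0.894
- Approximate test: z = atanh(L²/0.894) × √122; rejection = P(Z > 1.96 − z) + P(Z < −1.96 − z)

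For L = .4: .16/0.894 = .179; z = .181 × 11.05 = 2.00; rejection ≈ 52%.

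| L | corr(CARE, change) | chance of p < .05 |
|---|---|---|
| .1 | −.011 | 5% |
| .2 | −.045 | 8% |
| .3 | −.101 | 20% |
| .4 | −.179 | 52% |
| .5 | −.280 | 89% |

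Simulation agrees to within about one percentage point. If the model also adjusts for baseline, the correlation becomes −L²/√(1 − ρ²) = −L²/0.8, and L = .3, .4 and .5 give about 24%, 61% and 94%.

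**A different mechanism.** Let CARE depend directly on loneliness at the post session, with correlation −r. Then corr(CARE, change) = −r√((1 − ρ)/2). For r = .1, .2, .3, .4 and .5 this gives −.045, −.089, −.134, −.179 and −.224. In simulation the rejection rates are 8%, 17%, 32%, 51% and 71%.

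**Stable traits.** If CARE follows only stable loneliness, the trait enters pre and post alike and drops out of the difference. In simulation the change model rejects at about 5% for every r from .1 to .5. A baseline-adjusted model does not have this protection: rejection rises from about 8% to 66% over the same range.

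**Caller-level alternative.** With k callers, significance needs |r| = t/√(k − 2 + t²), where t is the two-sided 5% point on k − 2 degrees of freedom.
- k = 6: 2.776/√(4 + 7.71) = .81
- k = 4: 4.303/√(2 + 18.51) = .95

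**The case against.** The strongest reply is that the documents already limit the claim. The analysis is labelled exploratory, the goal is only to begin understanding, the Benefits section says the findings could help inform programmes, and *predicts* can be read as association. No endpoint or power statement rests on it. All of this stands and keeps the point modest. But *impact* of empathy on outcomes, and a use in identifying staff characteristics, go beyond association, and the analysis text sets no limit on how the coefficient may be read.

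The Toronto score is not forgotten either: it is among the sub-study goals, and the Benefits section describes exploring it alongside CARE and outcomes. That also stands. The gap is that the Data Analysis section gives it no role.

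Two stronger readings are tempting and are not supported:
- A reader might infer that the trial would probably report a spurious empathy finding. That depends on the loading, which the documents do not give. At .1 or .2 the rate is 5% to 8%, and even at .3 it is about 20%.
- A reader might infer that generally lonely people, or people who answer favourably in general, create the association. In the planned unadjusted change model such stable tendencies largely cancel. Only a state specific to the post session does the damage there.

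**Conclusion.** The point holds as a limit on interpretation. With one rating and one post outcome from the same session, the planned coefficient cannot separate an effect of caller empathy from a shared state on that occasion.

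The size is uncertain: with no true effect, the chance of a significant result runs from about 5% to 89% over assumed loadings of .1 to .5. These rates are false positives only for a causal reading, because the concurrent association itself is real in the model. The figures rest on the plan's n and ρ, on a state independent of baseline, and on the inference that CARE and the post scores share a session. The point does not concern the randomised comparison of the two arms.

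**What to change.** 1. In Data Analysis, describe own CARE against change, in the intervention arm, as a concurrent association. State that it will not be used to support *predicts*, the impact of caller empathy on outcomes (Sub-study exploration goals), or the choice of staff characteristics (Benefits).
2. Add the callers' Toronto score from before training and calls as the caller-level predictor. Report an estimate with its interval, described as hypothesis-generating.

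**Cost.** A few sentences and no new data. The Toronto analysis will be very imprecise: the documents give 4-6 callers (intervention arm description), 6 (Data Analysis) or 7 (Total Sample Size), and sub-study participation is optional. It may also be confounded, since no random allocation of participants to callers is described.

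**A substitute to avoid.** The mean CARE from the caller's other participants may look like a way round the problem. Within a caller with n participants it equals (caller total − own CARE)/(n − 1), an exact decreasing function of own CARE. With caller terms in the model, as Data Analysis plans, and equal panels, it is the own-CARE test with its sign reversed. Simulated rejection with no true effect was 19%, 51% and 88% at loadings .3, .4 and .5.
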